5.1 Primary endpoint - Tolerability

- The grade of any adverse events (AE) requiring medical intervention within three months of treatment should be low. Device-based treatment will be considered tolerable if less than 30% of participants treated have an "Overall AE Score" larger than Grade 2 AE at the 3month follow-up (visit 4) as assessed via Common Terminology Criteria for Adverse Events (CTCAE), U.S. Department of health and human services, Ver 5.0, Nov 27, 2017.
- The rate and nature of spontaneous healing of the treated cNF lesion and any safety related event including potential wound formation and wound healing should be equivalent to expectations from alternative method(s). Safety evaluation includes rating of treatment associated sequele by end of study, e.g. dyspigmentation and scarring and overall investigator rating compared to expectations.

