6.5 Participants

Study participants are recruited among the hospital patients of the two centers, invited out of the routine offering them different treatment options. Further recruitment may be made by direct referral of eligible patients after contact to other relevant hospital departments and centers or patient associations in these the respective countries.

Diagnosis of their cNF is according to standard routine of the hospitals. Confirmation of the neurofibromatosis syndrome by biopsy is not used in the routine since the disease is characteristic and commonly diagnosed by simple means e.g. history and clinical signs. Patients may have been evaluated genetically or not. Participants' enrolment as hospital patients continues along with their participation in the study.

Because most patients with NF1 and cNF wish many of their cNFs treated, there is no upper limit of number to be treated according to the protocol. The patient and the physician will decide the cNFs to be treated.

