6.5.3 Criteria and procedures for participant withdrawal or lost to follow up

- Exclusion criteria identical to non-inclusion criteria, however, appearing during the study.
- Patients acquiring disease of higher priority contraindicating their further participation or making participation not possible in practice.
- Patients' decision to leave the trial, irrespective of reason.
- Patients' non-adherence to the study schedule.
- Unforeseen hazards or significant clinical adverse events making continuation of the study not ethical.

6.5.4 Withdrawal from the Study

Each participant has the right to withdraw from the study at any time without prejudice. The investigator may discontinue any participant's participation for any reason, including failure to comply with the protocol (as judged by the investigator such as compliance below 80%, failure to maintain appointments, etc.).

Should a participant withdraw from the study, the reason(s) must be stated on the case report form, and a final evaluation of the participant should be performed.

Patients who go off treatment must be followed for AEs for at least 30 days from treatment or biopsy.

Reason for withdrawal from study is documented in the case report form. Withdrawals after HIFU treatment and before the 3-month visit are replaced and not included in the analysis of results (but registered as dropouts). Withdrawals after 3 months are replaced on investigators discretion.

6.5.5 Study Termination Criteria

The study may be terminated for multiple potential reasons. Some of these reasons include:

• Majority of participants experience severe and unbearable pain, on investigator's decision based on a minimum of 3 participants.

- Unbearable immediate wheal and flare reaction with severe itch and swelling and urticaria disseminating to larger skin areas experienced by a minimum 3 patients, on investigator's decision as indicated above.
- Any systematic (general or local) acute response to the treatment deemed by the investigator to be a clinically significantly different clinical or psychological reaction or adverse event than expected.
- The efficacy of the treatment is in the majority of participants at the 3-month interim assessment (visit 4) deemed to be unacceptably poor by the investigator or the sponsor. Unacceptable efficacy is defined as cure rate below 20% at the 3-month visit, based on a sample of minimum 8 participants in each group of the study.

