6.5.6 Participant enrollment and handling

Every effort will be made to arrange routine clinical follow-up for all participants, independent of how many study-associated visits they have completed.

Enrolment into study will take place at the two participating hospital departments (Department of Dermatology, Bispebjerg University Hospital and Department of Dermatology and Venereology, Sahlgrenska University Hospital).

The total duration of the study from enrolment of first participant to end of data collection is expected to be 1.5 years.

Expected total duration of each participants' participation is 9 months, with milestone evaluation after every 3 months.

In total 20 participants will be enrolled (target enrolment is 10 participants at Department of Dermatology, Bispebjerg University Hospital and 10 participants at Department of Dermatology and Venereology, Sahlgrenska University Hospital). Enrolment is not stratified. Limits can be changed based on the coordinating investigators discretion if recruitment to one study group turns out being not possible or according to experience unrealistic. Enrolment is based on participants remitted to the centers for diagnosis and treatment of NF1. Participants with urgent treatment need are not enrolled.

Participants of the study continue their course and normal registration in the hospital department. Each study visit is registered and documented in the hospital file parallel to registrations in the case reports of the study.

Histology taken at the Swedish center will be labeled using the study codes which do not contain the personal identification number of the study person. The samples will be used only for research purpose and not for patients care and treatment. The samples will be analyzed separately by a pathologist and the PI in Sweden. After the analyses the samples will be stored in Biobank Väst in Sahlgrenska Universitetssjukhuset,

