14.2 Serious Adverse Events

A serious adverse event (SAE) is any event that led to any of the following:

- a) death,
- b) serious deterioration in the health of the subject, that resulted in any of the following:
 - I. life-threatening illness or injury,
 - II. permanent impairment of a body structure or a body function,
 - III. hospitalization or prolongation of patient hospitalization,
 - IV. medical or surgical intervention to prevent life-threatening illness or injury or permanent impairment to a body structure or a body function,
 - V. chronic disease,
- c) foetal distress, foetal death or a congenital physical or mental impairment or birth defect

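### Required adverse-event follow-up after early withdrawal is a 30-day minimum, shorter than the three-month tolerability window, and those who leave before visit 4 are dropped from the analysis

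*Combined protocol and SAP*

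**What the plan says.** Treatment is one session on day 0 (Table 1). For those who stop, section 6.5.4 sets this minimum: "Patients who go off treatment must be followed for AEs for at least 30 days from treatment or biopsy". It also asks that on withdrawal "a final evaluation of the participant should be performed", without saying when or what it must contain.

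The same section settles the analysis: "Withdrawals after HIFU treatment and before the 3-month visit are replaced and not included in the analysis of results (but registered as dropouts". For later leavers, "Withdrawals after 3 months are replaced on investigators discretion".

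The primary endpoint in section 5.1 opens: "The grade of any adverse events (AE) requiring medical intervention within three months of treatment should be low". The criterion is that fewer than 30% of the participants treated have an Overall AE Score above Grade 2 at visit 4. A second part covers sequelae such as scarring and dyspigmentation, rated by end of study. Table 1 puts visit 4 at 12 ± 2 weeks and visit 6 at 39 ± 3 weeks.

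Three other provisions bear on the point:
- Section 7 has the grade recorded directly after treatment and at each later visit.
- Section 6.5.6 says: "Every effort will be made to arrange routine clinical follow-up for all participants, independent of how many study-associated visits they have completed".
- Section 16 leaves follow-up of device-related events to the investigator's discretion.

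**The concern.** The follow-up a site must provide is shorter than the period over which the primary endpoint is judged. No section requires the visit 4 score, or the end-of-study sequelae rating, from someone who has left.

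The loss may also be related to the outcome. Section 6.5.3 makes the non-inclusion criteria grounds for withdrawal when they appear during the study. In section 6.5.2 these include impaired wound healing and a tendency to keloid or hypertrophic scarring. Section 6.5.3 also lists significant clinical adverse events. A participant could therefore leave because of the kind of harm the endpoint is meant to count, and then be replaced by someone who tolerated treatment. The reported proportion would describe those who reached visit 4, whereas section 5.1 defines it among those treated.

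**Working it through.** **Plan's own figures.** The plan calculates nothing about follow-up length. Its precision formula reproduces: 1.96² × 0.90 × 0.10 / 0.15² = 15.37, rounded to 16. It matters here only because it supplies the planned event rate, 1 − 0.90 = 10%. Planned enrolment is 20.

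**Length of required follow-up** (Table 1; sections 6.3.2 and 6.5.4)
- Visit 4 is nominally day 12 × 7 = 84, with a window of days 70 to 98.
- Counted from treatment, the minimum covers 30/84 = 36% of the primary window (30/98 = 31% to 30/70 = 43%).
- Days without required follow-up: 84 − 30 = 54 (70 − 30 = 40 to 98 − 30 = 68).
- A Swedish participant leaving before visit 4 has at most the visit 3 biopsy, on days 4 to 10, so the minimum ends on days 34 to 40. Danish participants have no biopsy.
- A biopsy at a nominal visit 4 carries the minimum to 84 + 30 = day 114, but that participant has already reached the primary time point.
- No visit is scheduled between day 10 (latest visit 3) and day 70 (earliest visit 4), so day 30 coincides with no planned grading.
- The sequelae rating falls at 39 × 7 = day 273 (252 to 294).

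**Effect on the decision.** With 20 evaluable participants, 5 events pass (25%) and 6 do not, because 30% is not below 30%. Suppose *x* events are seen among the 20, and *w* replaced withdrawals all had Grade 3 or above. The rate among all treated is (*x* + *w*)/(20 + *w*).

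| Observed | Largest *w* that still passes | Smallest *w* that reverses the result |
|---|---|---|
| 5/20 (25%) | 1: 6/21 = 28.6% | 2: 7/22 = 31.8% |
| 4/20 (20%) | 2: 6/22 = 27.3% | 3: 7/23 = 30.4% |
| 2/20 (10%, as planned) | 5: 7/25 = 28.0% | 6: 8/26 = 30.8% |

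The values of *w* are assumptions: section 7 says only that low dropout is expected. The table applies the replacement rule of section 6.5.4. Section 6.6 describes replacement before the 3-month visit more narrowly, for voluntary or non-medical dropout, and the two should be made to agree.

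**The case against.** The strongest reply is that the sentence sets a minimum, not a limit, and that other cover exists. Grades up to withdrawal are on file, a final evaluation is expected, and section 16 allows device-related events to be followed with no fixed end. Section 6.5 adds: "Participants' enrolment as hospital patients continues along with their participation in the study". Anyone who leaves after visit 4 already has the primary score, and only the sequelae rating is then at risk.

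Most of this stands, and it rules out saying that follow-up stops at 30 days or that the outcome is never collected. It does not close the gap. The final evaluation has no date, and an evaluation on day 10 or day 35 is not a week-12 grade. Section 6.5.6 promises effort towards routine care, with no grading or CRF entry stated. Section 16 is discretionary and limited to device-related events.

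A second reply is that longer collection alone would leave the planned result unchanged, because withdrawals before the 3-month visit are excluded anyway. That is correct, and it is why the two rules must be changed together.

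Three stronger readings are tempting but not supported:
- *That one missing grade could decide the result.* If the withdrawal is not replaced, 5/19 would become 6/20 = 30.0%. Under the replacement rule in section 6.5.4, one omitted Grade 3+ case gives 6/21 and still passes.
- *That the relevant harms appear mainly after the first month.* The plan gives no onset times for infection or delayed healing, and does not suggest that scarring or pigment change would reach Grade 3.
- *That outcomes of a pregnancy arising after visit 4 would be lost.* Section 14.2 counts "foetal distress, foetal death or a congenital physical or mental impairment or birth defect" as serious, and the duty in section 14.4 to report related serious events has no 30-day limit. By then the primary score exists.

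**Conclusion.** The point holds as a mismatch between sections 5.1 and 6.5.4. Required follow-up for those who leave before visit 4 covers about 36% of the primary window (to days 34 to 40 after a visit 3 biopsy), and neither their visit 4 score nor their sequelae rating has to be obtained. The existing cover is partial. The exclusion rule is the larger threat to the primary result, because it removes these participants from the denominator that section 5.1 sets.

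The numerical effect depends on how close the result is to the limit. Two omitted Grade 3+ withdrawals reverse a 5/20 result, and six are needed at the planned 10% rate. If dropout is as low as the plan expects and events are as rare, the conclusion would probably not change. The plan gives no dropout rate with which to test that. The change should be made because it is cheap and some grounds for withdrawal are related to the endpoint.

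**What to change.** Reconcile section 6.5.4 with section 5.1 by making two changes together.

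1. State that, unless they refuse, every participant who received HIFU has AE data and the Overall AE Score collected to the visit 4 window, and sequelae to the end-of-study visit, whether or not they attend. If they do not attend, take the information by telephone or from the hospital file. Say what going off treatment means when there is only one session, and separate it from leaving the study.
2. Delete the exclusion of withdrawals before the 3-month visit from the tolerability analysis, so that all treated participants are in the denominator. Replacements may still be enrolled, but they should be added to those who left. For anyone who refuses, state in advance how the missing grade is counted.

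These use the plan's own time points. The cost is an amendment to the plan and consent wording, and a few calls or chart checks. A grade not based on an examination will be less precise, so its source should be recorded.

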Clinical recording of the study includes clinical assessment of healing and therapeutic effect on the tumors. Such assessment follows clinical criteria described in textbooks, guidelines and clinical consensus in the specialty of dermatology. Prior to study, the two investigator sites have coordinated their clinical assessment method.

The chosen 9-month total study period is considered acceptable for observation of tolerance and curative effect of HIFU for cNF with observation of primary therapeutic effect after 3 months. Assessments includes monitoring of the wound healing phase, observation of late recurrences, and observation of scarring.

The study includes no follow up medication, but the study can involve use of wound healing dressings and other remedies in the wound healing phase on investigators individual recommendation. The study involves no standard recommendation on post treatment care, which is anticipated to be simple.

After the study participants are followed in the respective hospital departments according to their needs and the department routines.

Participants who drop out of the study before the 3-month visit voluntarily or for non-medical reasons, including non-adherence, will be replaced by new participant(s). Withdrawals after 3 months are replaced on investigators discretion with considerations to the impact of the overall investigation schedule.

Patient with incomplete cure documented by ultrasound imaging assessment or biopsy and histology after 3 months or subsequent control visit (indicated by clinical suspicion of reoccurrence) will be offered a second treatment based on the standard treatment offered by the center. The specific treatment will be decided by the investigator and the patient based on the extent and severity of the recurrence.

The study will conclude when all participants have completed the 9-month study period, when all data are on file, and the statistical analysis is concluded. Interim analysis of data collected after 3 months and later is allowed, per investigator's decision.

If the study design is deemed inferior, the protocol can be amended.

The study produces no physical test samples relevant for purposes outside the study.

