6.7 Monitoring plan

The study will be monitored separately in the two centers. In Denmark, it is intended that the study is monitored by GCP-enheden ved Københavns Universitetshospital. In Sweden, the study is intended to be monitored by Gothia Forum for Clinical Studies. Both are units serving the respective regional healthcare researchers.

As the monitoring unit in the region of the sponsor's center, the Danish GCP unit will have the responsibility to coordinate a shared monitoring plan, where each party monitors the investigation center. The monitoring plan will be made with due consideration to the centers designated tasks and reflect considerations to specific risks in the tasks performed.

An overview of monitoring activities and focus-areas are given in Table 4.

Investigation activity	Stage / Visit	GCP Unit KU, DK	Gothia Forum, SE
Monitoring plan	Before	Х	(x)
Initiation of study	Before	Х	Х
Recruitment	Before	Х	Х
Screening and inclusion/exclusion	Visit 1	Х	Х
Selection and documentation of lesions for treatment	Visit 2	Х	Х
HIFU Treatment	Visit 2	Х	Х
Post treatment documentation and evaluation by investigator and patient	Visit 2	Х	Х
Follow-up visits with documentation and evaluation by investigator and patient	Visit 3 - 6	Х	Х
Ultrasound scanning – Procedure and analysis from measurements	Visit 2 – 6	Х	
Biopsies – Procedure and analysis from pathological report	Visit 2 – 4		Х
CRF entry and REDcap	Visit 1 - 6	Х	Х
Statistical analysis	After		Х
Study Reporting	After	х	
Close of study – Archive readiness	After	Х	Х

lable 4. Monitoring	activities in the two	o monitorina unite	s used by the	e investigation centers.

7 Statistical design and analysis

The number of patients recruited for participation in the study will be balanced with due consideration to ethical aspects and the statistical background for conclusive statements regarding the primary endpoint.

As mentioned above, the primary endpoint of the study is to document the tolerability and safety profile of the treatment. As the main measurable endpoint, the grade of overall adverse effects following treatment is best suited for evaluation of participants in the study. The measurement of this endpoint is done subjectively by the investigator according to a conventional grading system, and is measured directly after treatment and at all subsequent control visits. The input template for measurement is illustrated in Fig. 7.

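### Treated participants who withdraw before the 3-month visit are replaced and dropped from the analysis, although the tolerability limit is set on all treated; if withdrawal is linked to adverse events, the Grade 3+ proportion is biased towards a pass

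*Combined protocol and SAP*

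**What the plan says.** Section 5.1 calls the treatment tolerable if "less than 30% of participants treated" have an overall AE score above Grade 2. It gives two timings: adverse events in the three months after treatment, and the score at visit 4. Section 7 adds that the overall grade "is measured directly after treatment and at all subsequent control visits".

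Section 6.5.4 sets the rule for early leavers: "Withdrawals after HIFU treatment and before the 3-month visit are replaced and not included in the analysis of results (but registered as dropouts". It makes no exception for a safety-related reason. Among the grounds for withdrawal in section 6.5.3 are the patient's "decision to leave the trial, irrespective of reason" and any exclusion criterion that appears during the study. Impaired wound healing is one of the exclusion criteria in section 6.5.2.

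For leavers, section 6.5.4 says that "a final evaluation of the participant should be performed" and that "Patients who go off treatment must be followed for AEs for at least 30 days from treatment or biopsy".

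Section 6.6 has a narrower replacement rule: "Participants who drop out of the study before the 3-month visit voluntarily or for non-medical reasons, including non-adherence, will be replaced by new participant(s". It does not say who is analysed. Section 7 defines no analysis set and no sensitivity analysis for withdrawals.

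**The concern.** The endpoint's denominator is everyone treated, but the analysis rule removes some of those people after treatment, when their adverse events may already be known. A participant who leaves because of a bad reaction, or because a wound fails to heal, is taken out of the proportion meant to count such outcomes. A new participant takes the place. If this happens more often to Grade 3+ participants than to others, the reported rate is too low.

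The distortion is largest when the true Grade 3+ rate is near or above the limit, which is where the limit has to work. With 20 analysed participants, a couple of cases can decide the result.

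**Working it through.** **Inputs from the documents.** 20 participants (sections 6.5.6 and 7). Limit: below 30% Grade 3+ (section 5.1), so at most 5 of 20 passes. Planned Grade 3+ rate: 10%, since section 7 takes P = 0.90 for Grade 2 or lower. Drop-out: expected to be low, with no figure.

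**The plan's own figure.** Section 7 gives N = 1.96² × 0.90 × 0.10 / 0.15² = 15.37, rounded up to 16. This reproduces (15.366). It makes no allowance for withdrawals, and the plan states no figure for their effect.

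**Expected analysed rate.** Let p be the true Grade 3+ rate among all treated, s the share of Grade 3+ participants who leave before visit 4, and r the share of the others who leave. Under section 6.5.4 the expected analysed rate is

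q = p(1 − s) / [p(1 − s) + (1 − p)(1 − r)].

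The values of s and r are assumptions.

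| p | s | r | q |
|---|---|---|---|
| 30% | 5% | 0 | 0.285/0.985 = 28.9% |
| 30% | 10% | 0 | 0.270/0.970 = 27.8% |
| 30% | 25% | 0 | 0.225/0.925 = 24.3% |
| 30% | 25% | 10% | 0.225/0.855 = 26.3% |
| 30% | 10% | 10% | 0.270/0.900 = 30.0% (no bias) |
| 10% | 25% | 0 | 0.075/0.975 = 7.7% |

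At p = 30% and r = 0, the expected number of leavers per 20 completers is 20ps/(1 − ps): 0.3, 0.6 and 1.6 for s = 5%, 10% and 25%.

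**Counts that reverse the result** (20 analysed, k excluded Grade 3+ cases put back):
- 5/20 = 25.0% passes. With k = 2 it is 7/22 = 31.8%, a fail; k = 1 gives 6/21 = 28.6%, still a pass.
- 4/20 needs k = 3 (7/23 = 30.4%).
- 3/20 needs k = 5 (8/25 = 32.0%).
- 2/20, the count expected at the planned rate, needs k = 6 (8/26 = 30.8%).

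If medical leavers are not replaced, as section 6.6 can be read, but are still excluded, one case is enough: 6/20 = 30.0% fails and 5/19 = 26.3% passes.

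**At the planned 10% rate**, with X ~ Bin(20, q) and a pass at X ≤ 5, the pass chance is 98.9% without withdrawals and 99.7% with s = 25%. The rule hardly matters there.

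**Why pass chances are a poor measure of the bias.** At a true 30% rate with no withdrawals, the pass chance is 41.6% with 20 participants, 55.1% with 21 and 49.4% with 22, only because the allowed count moves in whole steps. With s = r = 10% there is no bias, yet the pass chance is 41.6% under section 6.5.4 and 49.7% when all treated are counted. The expected rate q and the reversal counts do not have this flaw.

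**The case against.** The strongest reply is that the effect is probably small. Treatment is a single session, drop-out is expected to be low, and at s = 5% to 10% the expected rate moves only from 30% to 28.9% or 27.8%. Adverse effects are categorised at every visit as a secondary safety endpoint (section 5.2), and dropouts and their reasons are recorded. The 6.5.3 item on "significant clinical adverse events making continuation of the study not ethical" may concern stopping the study rather than one person's withdrawal. All of this stands and limits the size. None of it returns a withdrawn participant to the primary proportion, and a voluntary exit prompted by an adverse event is replaced under both 6.5.4 and 6.6.

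A second reply is that counting all treated can also mislead. A leaver with no recorded Grade 3+ who is entered as a non-event turns 6/20 = 30.0% (fail) into 6/21 = 28.6% (pass). Grading leavers on any earlier Grade 3+ but completers at visit 4 only would be uneven. Both points are correct and shape the fix.

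A reader might infer that the rule makes a false pass likely. With s = 50% or 75% at a true 30% rate, the pass chance would be 87.4% or 99.0%. That needs 3.5 or 5.8 Grade 3+ leavers per 20 completers, and the documents give no support for such numbers. A reader might also infer that leavers' adverse events go unreported. The documents do not say so; they remove leavers from the analysis, not from AE recording.

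**Conclusion.** The rule is wrong as written. Section 6.5.4 excludes people whom the section 5.1 denominator includes, and no other section puts them back. The conflict in the text is certain; the bias is conditional. It arises only if Grade 3+ participants leave before visit 4 more often than others. At a true 30% rate it lowers the expected analysed proportion by 1.1, 2.2 or 5.7 percentage points for s = 5%, 10% or 25% with all others staying. Two excluded cases can reverse a 5/20 result. The effect is negligible at the planned 10% rate.

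These figures treat Grade 3+ status as fixed, so that each excluded case would have counted at visit 4. Part of the false-pass risk at a true 30% comes from judging a point estimate on 20 participants, which changing the analysis set does not cure.

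Sections 5.1 and 7 also word the limit differently (strictly below 30%, or up to and including 30%). That is a separate item to reconcile, and its looser form should not be used to enlarge this point.

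**What to change.** 1. Define the primary tolerability set as all participants who receive any HIFU. Replacements add to the denominator and never stand in for a treated participant.
2. Reconcile the two timings in section 5.1 first. Then grade leavers and completers by the same rule, for example the worst recorded overall AE grade from treatment to visit 4; the score is already taken at every visit.
3. Do not silently count a leaver with incomplete follow-up and no recorded Grade 3+ as a non-event. Report the proportion with best-case and worst-case bounds, and claim tolerability without qualification only if both give the same conclusion. For example, 5/20 completers plus two such leavers gives 5/22 = 22.7% to 7/22 = 31.8%, which would need qualification.
4. As sensitivity analyses, count AE-related withdrawal as failure, and report completers only.
5. Reconcile sections 6.5.4 and 6.6 on who is replaced.

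**Cost.** Wording in sections 5.1, 6.5.4, 6.6 and 7, with no added visits. The reported rate may be slightly less favourable, and the denominator may exceed 20. A worst-grade rule would also be stricter for completers than a visit-4 rule, so the choice should be fixed before data are seen. Some leavers will have AE data for only about 30 days, short of the 12-week visit, so the bounds will not always be tight.
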